7.4.2.5. DRC Assessments

Reasons for treatment failure according to DRC classifications (i.e. blood cultures did not become negative, or additional antifungals given, or died, or withdrew from study but did not die) will be summarized descriptively at EOST and EOT visits for the MITT and PP populations.

Reasons for relapse or other reasons for not having an outcome of sustained success at follow-up according to DRC classifications, will be summarized descriptively at 2 and 4 weeks after EOT for the MITT and PP populations.

Reasons for death according to DRC classifications (i.e. candidemia probably contributory, candidemia probably not contributory, or not known) will be tabulated for the MITT and PP populations.

7.4.3. Exploratory Efficacy Analysis

Change in serum (1,3)- β -D-glucan levels from Baseline (pre-dose) to EOST will be summarized in total with descriptive statistics for the MITT Population.

Correlation of blood culture and T2MR assay Candida spp. results from Baseline (pre-dose) through EOST will be explored. The number and percentage of patients with different Candida spp. isolated from blood culture and Candida spp. results from T2MR assay will be summarized by each visit from Baseline (pre-dose) through EOST for the MITT Population.

7.4.4. Other Efficacy Data

All other efficacy data will be listed by patient.

7.5. Safety Analysis

All safety analyses will be performed on the Safety Population.

7.5.1. Adverse Events

AEs will be captured from the date of informed consent through study completion. All AEs will be coded to system organ class and preferred term using the MedDRA, Version 20.1. TEAEs are defined as AEs that start on or after the administration of study drug.

An overview of AEs will be provided including counts and percentages of patients (and event counts) with the following:

- Any AEs;
- Any TEAEs (overall and by maximum severity);

- Any study drug-related TEAEs (overall and by maximum severity);
- Any serious AEs (SAEs);
- Any treatment-emergent SAEs (TESAEs);
- Any study drug-related treatment-emergent SAEs (TESAEs);
- Any TEAEs leading to discontinuation of study drug;
- Any study drug-related TEAEs leading to discontinuation of study drug;
- Any AEs leading to discontinuation of study;
- Any study drug-related TEAEs leading to discontinuation of study; and
- Any AEs leading to death.

The number and percentage of patients who experienced at least one TEAE will be presented by system organ class and preferred term. Drug-related TEAEs, study drug withdrawals due to TEAEs, and all SAEs will be summarized in the same manner.

Summaries will be provided by worst grade for the number and percentage of patients with TEAEs and for patients with drug-related TEAEs by system organ class and preferred term.

Although a patient may have two or more TEAEs, the patient is counted only once within a System Organ Class and Preferred Term category. The same patient may contribute to two or more preferred terms in the same System Organ Class category or to two different System Organ Class categories.

A list of patients who have serious adverse events (SAEs), a list of patients who discontinue from study drug due to TEAEs, and a list of death due to AEs will be provided. All adverse events will be listed.

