5.6.3 Step-down Antifungal Therapy

The IDSA clinical practice guidelines for treatment of Candidiasis recommend that the total duration of therapy for candidemia is 14 days after documented clearance of *Candida* spp. from the bloodstream (i.e., first consecutive negative blood culture) and resolution of symptoms attributable to candidemia. Hence, the duration of antifungal treatment required to treat patients with candidemia in this study will be driven by the time to clearance of candidemia. In 3 randomized controlled trials in candidemia and invasive Candidiasis, the median time to bloodstream infection clearance after receiving appropriate antifungal therapy was 2 to 3 days. Therefore, patients enrolled in this study may need a few additional days of fluconazole therapy for a total duration of antifungal treatment of approximately 16 to 17 days. Likewise, any patients who have deep-seated sites of infections diagnosed after enrollment, while they can continue to receive APX001 study drug treatment per protocol, will require additional days of fluconazole therapy.

If appropriate, additional antifungal drug therapy with fluconazole (unless susceptibility results warrant alternative antifungal therapy) can be administered beyond 14 days of APX001. The recommended dose of fluconazole is 800 mg QD on the first day followed by 400 mg QD, for a maximum of 7 days.

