9.2.2 Analysis of Safety

All safety analyses will be performed on the Safety Population. Safety data will be patient to clinical review and summarized by appropriate descriptive statistics. A DSMB will be assigned to monitor safety on an ongoing basis throughout the study.

Analyses will be based on adverse events, vital signs, clinical laboratory assessments, and ECGs. Safety analyses will be descriptive and will be presented in tabular format with the appropriate summary statistics.

A TEAE is defined as an adverse event started on or after the administration of study drug. The number and percentage of patients with TEAEs will be tabulated by system organ class, preferred term, and by severity and relationship to treatment. Serious adverse events and adverse events leading to discontinuation from study drug will be summarized. Listings will also be provided for SAEs and adverse events leading to discontinuation of study drug.

Descriptive statistics will be provided for clinical laboratory data for both actual values and changes from Baseline over time.

Descriptive statistics will be provided for vital sign data presented as both actual values and changes from Baseline over time.

Abnormal physical examination findings will be listed.

Descriptive statistics will be provided for ECG interval data and presented as both actual values and changes from Baseline.

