2.2. Study Design

This is a multicenter, open-label, non-comparative, single-arm study to evaluate the efficacy and safety of APX001 for the first-line treatment for candidemia including suspected or confirmed antifungal-resistant candidemia in non-neutropenic patients ≥ 18 years of age. Suspicion of antifungal-resistant candidemia is sufficient and subsequent documented resistance is not required for enrollment. The Study Drug Treatment Period will be up to a maximum of 14 days (inclusive of the loading dose [Study Day 1]). After completion of 14 days study drug therapy, if further antifungal treatment is indicated to complete treatment of candidemia in accordance with standard practice guidelines, fluconazole (unless susceptibility results warrant alternative antifungal therapy) may commence for up to a further 7 days. There will be a Follow-up Period of 4 weeks (+4 days) after EOT/EOST. The total duration of participation in the study is up to approximately 7.5 weeks (inclusive of the Screening Period [≤ 96 hours prior to Baseline]).

Patients with a yeast identified in a blood culture or a positive rapid diagnostic method are eligible to be consented and screened for the study. Patients must have at least 1 positive blood test for *Candida* species (spp.) (or yeast suspected to be *Candida*) for a diagnosis of candidemia to be considered for enrollment into the study. Patients with a positive blood culture showing yeast suspected to be *Candida* must have identification of *Candida* spp. from positive blood culture confirmed prior to dosing. Screening and Baseline procedures and the start of APX001 study drug will be initiated within 96 hours from the time that the SOC blood sample for the *Candida* spp. positive culture or rapid diagnostic test was drawn.

Patients with >2 days (>48 hours) equivalent of prior systemic antifungal treatment at approved doses to treat the current episode of candidemia within 96 hours before first dose will be excluded. However, patients with *Candida* infections proven to be resistant to the specific antifungal administered may have received ≤ 5 days (≤ 120 hours) equivalent of that prior treatment (results of susceptibility testing are required prior to enrollment).

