6.5.4. Intravascular Catheter Management and Log

If possible, all indwelling intravascular catheters should be removed and the catheter tips cultured prior to starting APX001 dosing. The entrance site should also be cultured if it appears infected. Intravascular catheter management should be managed at the site level as per local SOC.

6.6. **Safety Endpoints**

Safety assessments will include adverse events, vital signs, clinical laboratory evaluations, physical examination, and ECGs.

6.6.1. **Adverse Events**

An adverse event is defined as any untoward medical occurrence in a clinical investigation patient administered a pharmaceutical product, which does not necessarily have a causal relationship with this treatment. An adverse event can therefore be any unfavorable and/or unintended sign (including an abnormal laboratory finding), symptom, or disease temporally associated with the use of a study drug, whether or not related to the study drug. All adverse events, including observed or volunteered problems, complaints, or symptoms, are to be recorded on the appropriate eCRF.

6.6.2. **Clinical Laboratory Evaluations**

Screening laboratory assessments to determine eligibility will be performed at the local laboratory and may have been collected as SOC within the previous 24 hours. Laboratory assessments collected after Screening will be sent to the central laboratory for analysis.

Clinical laboratory assessments (serum chemistry, hematology, coagulation, and urinalysis) will occur at Screening, Baseline (pre-dose), twice weekly during Study Drug Treatment, at EOST, EOT, and 2 and 4 weeks after EOT, or Early Termination. If clinically indicated and at the discretion of the Investigator, or if a suspected adverse event is identified, clinical laboratory assessments may be conducted at any time during the study and compared to Baseline. The following is a complete list of clinical laboratory analytes.

Standard Safety Chemistry Panel

Alanine aminotransferase	Albumin			
Alkaline phosphatase	Amylase			
Aspartate aminotransferase	Bicarbonate			
Bilirubin (total, direct, and indirect)	Blood urea nitrogen			
Calcium	Chloride			
Creatine kinase	Creatinine			
Estimated glomerular filtration rate	Gamma-glutamyl transferase			
Glucose	Inorganic phosphorus			
Lactate dehydrogenase	Lipase			
Potassium	Sodium			
Total protein	Uric acid			
Hematology				

Hematology

Hematocrit
Platelets
White blood cell count and differential [1]

Hemoglobin Red blood cell count

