7.5.2. Clinical Laboratory Tests

Central laboratory test results (chemistry, hematology, coagulation, and urinalysis) at each scheduled visit and change from baseline will be summarized with descriptive statistics.

Shift tables from baseline to each scheduled post-baseline visit will be provided for selected chemistry parameters (ALT, AST, ALP, Total Bilirubin, Creatinine, and Creatinine Kinase) and hematology parameters (Hematocrit, Hemoglobin, Platelets, White blood cell count and differential). For chemistry parameters, the following categories will be used: < the lower limit of normal (LLN), normal, >ULN to $\leq 2 \times ULN$, $\geq 2 \times ULN$ to $\leq 3 \times ULN$, $\geq 3 \times ULN$ to $\leq 5 \times ULN$, $\geq 5 \times ULN$, and missing. For hematology parameters, the following categories will be used: low, normal, high, and missing.

The number and percentage of patients with the following potentially clinically significant abnormal liver function tests at any post-baseline visit will be summarized:

- ALT \geq 3×ULN;
- ALT \geq 5×ULN;

- ALT $\geq 10 \times ULN;$
- AST \geq 3×ULN;
- AST \geq 5×ULN;
- AST $\geq 10 \times ULN;$
- ALT or AST \geq 3×ULN;
- Total Bilirubin >1.5×ULN;
- Total Bilirubin >2×ULN;
- ALP \geq 1.5×ULN;
- ALP $\geq 2 \times ULN$;
- ALT or AST \geq 3×ULN and Total Bilirubin >1.5×ULN;
- ALT or AST \geq 3×ULN and Total Bilirubin >2×ULN; and
- Potential Hy's Law cases: ALT or AST \ge 3×ULN and Total Bilirubin >2×ULN, and ALP \le 2×ULN

A listing of patients with any post-baseline clinically significant abnormal liver function tests will be presented.

All clinical laboratory data will be listed. Values outside the normal ranges will be flagged.

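### Overall TEAE/SAE rates and any-visit liver-outlier counts pool the APX001, step-down and follow-up periods, and no AE table or combined liver criterion is split by period

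*SAP*

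**What the plan says.** Both documents define treatment emergence by its start alone. SAP 7.5.1: "TEAEs are defined as AEs that start on or after the administration of study drug". Protocol 9.2.2: "A TEAE is defined as an adverse event started on or after the administration of study drug". The collection period then sets the end of the window in practice: "AEs will be captured from the date of informed consent through study completion" (SAP 7.5.1).

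SAP 7.5.2 lists 14 liver criteria, from ALT at 3×ULN up to potential Hy's Law, and says that patients with "potentially clinically significant abnormal liver function tests at any post-baseline visit will be summarized". Under SAP 6.6.2, laboratory tests are taken "twice weekly during Study Drug Treatment, at EOST, EOT, and 2 and 4 weeks after EOT, or Early Termination".

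The treatment sequence is in SAP 2.2. For APX001: "The Study Drug Treatment Period will be up to a maximum of 14 days". Then, if indicated, fluconazole or an alternative "may commence for up to a further 7 days". Follow-up is 4 weeks (+4 days). Protocol 5.6.3 anticipates that patients "may need a few additional days of fluconazole therapy for a total duration of antifungal treatment of approximately 16 to 17 days".

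Four parts of the plan bear on attribution:

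- SAP 7.5.1 tabulates drug-related TEAEs separately.
- SAP 7.5.2 summarizes laboratory values by scheduled visit.
- SAP 7.5.2 gives by-visit shift tables for selected analytes.
- All AEs and laboratory data are listed.

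**The concern.** Safety shares the primary objective with efficacy, and the number of patients with TEAEs is a listed endpoint. There is no control arm, so the only handle on what belongs to APX001 is timing and investigator judgement. A headline rate that runs to study end mixes three situations: on APX001, on a second antifungal after APX001, and on neither.

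The plan already keeps the first two apart elsewhere. Efficacy at EOST allows no other systemic antifungal, while efficacy at EOT allows step-down (SAP 6.4.1 and 6.4.2). Exposure is reported for study drug and, separately, for overall antifungal treatment (both under SAP 7.3.6). The AE tables have no matching split. With about 20 patients, each patient moves a rate by 1/20 = 5 percentage points, so a few late events would visibly change the reported figure.

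**Working it through.** **1. Reproduce the plan's own duration.** Screening 4 d (96 h) + APX001 14 d + step-down 7 d + follow-up 28 d = 53 d = 7.57 weeks, against the stated approximate 7.5 weeks (52.5 d). It reproduces. With the +4-day visit window the sum is 57 d = 8.14 weeks.

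**2. Length of the TEAE window.** T = APX001 days + step-down days + follow-up days. Share after APX001 = 1 − 14/T, for a patient with the full 14 days of APX001 and complete follow-up.

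| Step-down | Follow-up | T | Share after APX001 |
|---|---|---|---|
| 0 d | 28 d | 42 d | 1 − 14/42 = 67% |
| 0 d | 32 d | 46 d | 1 − 14/46 = 70% |
| 2 d | 28 d | 44 d | 1 − 14/44 = 68% |
| 3 d | 32 d | 49 d | 1 − 14/49 = 71% |
| 7 d | 28 d | 49 d | 1 − 14/49 = 71% |
| 7 d | 32 d | 53 d | 1 − 14/53 = 74% |

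The range is 67-74%. It is calendar time at full dosing. A patient who stops APX001 early but completes follow-up has a larger share; one who dies or withdraws early has a shorter window.

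**3. Laboratory visits are distributed differently.** Twice weekly over 14 days is about 4 visits, plus EOST = about 5. Later visits are 2 weeks and 4 weeks after EOT, plus EOT itself when step-down is given = 2 to 3. So about 5 of 7 (71%) or 5 of 8 (63%) scheduled post-baseline laboratory visits fall at or before EOST. EOT tests need not be repeated when EOT is within 48 hours of EOST (Protocol 6.4.4), so short step-down leaves 2 later visits.

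**4. What pooling could do to an AE rate (illustration only).** The documents give no background event rate. Assume a constant background hazard unrelated to any drug, with 14-day risk p, and full follow-up of 20 patients. Risk over T days = 1 − (1 − p)^(T/14).

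| 14-day risk | 42 d | 49 d | Expected patients of 20: 14 d → 42 d → 49 d |
|---|---|---|---|
| 5% | 14% | 16% | 1.0 → 2.9 → 3.3 |
| 10% | 27% | 31% | 2.0 → 5.4 → 6.2 |
| 20% | 49% | 54% | 4.0 → 9.8 → 10.8 |
| 40% | 78% | 83% | 8.0 → 15.7 → 16.7 |

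If the hazard falls as patients recover, the increase is smaller.

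**5. Would a post-dose cut-off be enough?** The one post-dose limit found is the 30-day SAE reporting limit in Protocol 8.3, which governs reporting and not analysis. After a full course it runs to about day 14 + 30 = 44. That still covers every step-down day (15 to 21) and comes close to study end without step-down (day 42 to 46). A split by period is needed; a cut-off alone would change little.

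**The case against.** The case for leaving the plan alone has real weight.

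- **Laboratory data are partly split already.** By-visit summaries and shift tables show single analytes at EOST, EOT and each follow-up visit. An ALT rise first seen at EOT appears at EOT and not at EOST. This stands, so a reader should not infer that no planned summary separates the periods. What remains unsplit is the set of any-visit counts. The by-visit tables cannot show ALT or AST together with bilirubin in the same patient, and the shift bands stop at 5×ULN, so the 10×ULN criteria are not visible there either.
- **Related-TEAE tables filter by cause.** Protocol 8.1.3 accepts an event as related only if no other cause can be identified, so an event explained by fluconazole should drop out. This is a partial remedy. It rests on open-label judgement and not on time, and it may work differently once a second antifungal offers an alternative explanation.
- **Counting to study end is conservative.** This stands. Patients are counted over a fixed Safety Population, so a longer window can hold or raise a count but never lower it. The inference that late events dilute an on-APX001 signal is not supported; the direction is overstatement.
- **The SAP does not attribute potential Hy's Law cases to APX001.** It counts them by laboratory criteria and lists patients with abnormal liver tests. It would be wrong to say that a case arising at EOT would be reported as caused by APX001.
- **Step-down is not certain.** The protocol says patients may need it, at the investigator's discretion. Up to 48 hours of prior antifungal is allowed, so part of the clearance time may precede APX001. Step-down is likely for many patients, but the documents do not establish it for the typical patient.
- **The late period may still matter for APX001.** PK is sampled up to 2 weeks after EOT, so delayed effects are possible. This is a reason to keep the overall tables, not a reason against the split.

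**Conclusion.** The point holds for the overall TEAE and SAE rates and for the any-visit liver counts. They combine up to 14 days of APX001 with up to 7 days of step-down and 28 to 32 days of follow-up, they can overstate what occurred on APX001, and they cannot be read as APX001 rates. The 67-74% figure assumes 14 days of APX001 and complete follow-up. A reader might take it as the share of events or liver findings arising off drug; the documents give no event timing, and about 5 of 7 to 8 laboratory visits fall at or before EOST.

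The two documents agree on the definition, so this is not a contradiction. TEAEs leading to study drug discontinuation are tied to the APX001 period by nature and are not affected. The listings would allow a split later, but one chosen after the data are seen. This is an inexpensive improvement to a descriptive plan, best settled before database lock.

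**What to change.** Keep the overall tables as planned, and add two things.

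1. **SAP 7.5.1:** present TEAEs, related TEAEs and treatment-emergent SAEs by onset period: (a) first APX001 dose through EOST; (b) after EOST through EOT, for patients given step-down; (c) after EOT. Patients without step-down pass from (a) to (c). Give the number of patients entering each period, and state that (b) reflects APX001 followed by step-down.
2. **SAP 7.5.2:** show the liver-outlier and potential Hy's Law counts for post-baseline visits through EOST beside the any-visit counts.

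The cost is a few extra columns from dates already collected. The drawbacks are small counts in each column, and that delayed APX001 effects fall in (b) and (c). The second is why the overall tables stay.

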6.3 Screening (≤96 Hours Prior to Baseline)

The following procedures will be performed at Screening:

- Obtain informed consent
- Review inclusion/exclusion criteria
- Record medical history
- Record demography information
- Record vital signs, including temperature, blood pressure, heart rate, respiratory rate, oxygen saturation, and weight
- Intravascular catheter management and log of the line changes, to include any catheter tip culture results
- Perform dilated fundoscopic examination
- Perform clinical laboratory assessments (serum chemistry, hematology, coagulation, and urinalysis)
- Perform urine pregnancy test (for females of childbearing potential only)

- Collect blood cultures for *Candida* spp. (2 consecutive sets [1 aerobic and 1 anaerobic blood culture bottle per set] of blood cultures from 2 separate sites [1 from a central venous catheter (CVC) and 1 peripheral venipuncture, or 2 peripheral venipunctures, if a CVC is not applicable])
- Collect other cultures and histopathology from other sites, as clinically indicated to assess the site(s) and extent of candidemia infection
- Perform imaging tests as clinically indicated to assess the site(s) and extent of candidemia infection
- Record prior/concomitant medications
- Record adverse events

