8 SAFETY ASSESSMENTS

8.1 Adverse Events

An adverse event is defined as any untoward medical occurrence in a clinical investigation patient administered a pharmaceutical product, which does not necessarily have a causal relationship with this treatment. An adverse event can therefore be any unfavorable and/or unintended sign (including an abnormal laboratory finding), symptom, or disease temporally associated with the use of a study drug, whether or not related to the study drug. All adverse events, including observed or volunteered problems, complaints, or symptoms, are to be recorded on the appropriate eCRF.

Adverse events, which include clinical laboratory test variables, will be monitored and documented from the time of informed consent until study participation is complete. Patients should be instructed to report any adverse event that they experience to the Investigator. Beginning with Day 1 of study drug, Investigators should make an assessment for adverse events at each visit and record the event on the appropriate adverse event eCRF.

Wherever possible, a specific disease or syndrome rather than individual associated signs and symptoms should be identified by the Investigator and recorded on the eCRF. However, if an observed or reported sign or symptom is not considered a component of a specific disease or syndrome by the Investigator, it should be recorded as a separate adverse event on the eCRF. Additionally, the condition that led to a medical or surgical procedure (e.g., surgery, endoscopy, tooth extraction, or transfusion) should be recorded as an adverse event, not the procedure.

Any medical condition already present at Screening should not be reported as an adverse event unless the medical condition or signs or symptoms present at Baseline change in severity or seriousness at any time during the study. In this case, it should be reported as an adverse event.

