7.1.2. Handling of Dropouts and Missing Data

Subjects who dropped out or had missing outcome data will be included in the denominator for efficacy analyses. A clinical failure occurring at an earlier time point will be carried forward to the subsequent visits.

In cases of missing or incomplete dates (e.g. Adverse event [AE] and concomitant medications), the missing component(s) will be assumed as the most conservative value possible. For example, AEs with missing start dates, but with stop dates either overlapping into the treatment period or missing, will be counted as treatment-emergent, taking the worst-case approach. When partial dates are present in the data, both a partial start date and/or a partial stop date will be evaluated to determine whether it can be conclusively established that the AE started prior to the start of study drug or ended prior to the start of study drug. If the above cannot be conclusively established based on the partial and/or present dates, then the AE will be considered as treatment-emergent. Actual data values as they appear in the original eCRF will be presented in the data listings.

Missing values for other variables will not be imputed and only observed values will be used in data analyses and summaries.

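### TEAE status depends on start date alone, so an adverse event that begins between consent and first dose and worsens on APX001 falls outside the TEAE outputs unless the site re-records it

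*SAP*

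**What the plan says.** Both documents define treatment emergence by onset. SAP 7.5.1: "TEAEs are defined as AEs that start on or after the administration of study drug". Protocol 9.2.2: "A TEAE is defined as an adverse event started on or after the administration of study drug". Neither has a clause for events that start earlier and get worse on treatment.

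Events with pre-dose onset will be in the database: "AEs will be captured from the date of informed consent through study completion" (SAP 7.5.1).

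Protocol 8.1 does have a worsening rule, but it is a reporting rule and its subject is pre-existing conditions: "Any medical condition already present at Screening should not be reported as an adverse event". An exception follows for a condition, sign or symptom that later becomes more severe or more serious, which is then reportable. The section does not say which start date such an event should carry. Protocol 8.1.3 defines both causality categories by reference to the event either occurring or worsening after study drug.

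The number of patients with TEAEs is listed among the secondary endpoints (Protocol 7.2, SAP 6.2). The planned sample is approximately 20 patients in a single arm (SAP 2.2 and 3). SAP Section 9 states that nothing departs from the protocol's analysis.

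**The concern.** In a single-arm safety study of acutely ill patients, an event that was mild before dosing and becomes severe on drug is something the incidence tables ought to show. Under an onset-only rule it does not reach them if its pre-dose onset is known and it stays on its initial record.

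The result is also uneven. A condition present at Screening that worsens on drug becomes a reportable AE, and it is a TEAE if dated from the worsening. An AE that begins a little later, after consent but before dosing, and worsens in the same way has no rule that brings it in. An investigator may judge that worsening related to APX001, yet every drug-related row in SAP 7.5.1 is limited to TEAEs.

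Study-drug discontinuation is affected too. Protocol 9.2.2 promises a summary and a listing of adverse events leading to discontinuation of study drug, without restricting them to TEAEs. SAP 7.5.1 restricts both the table and the dedicated listing to TEAEs. A pre-dose AE that worsens and ends treatment would be in neither.

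**Working it through.** The documents give no TEAE rate or sample-size calculation to reproduce. The check applies the written rule to each case and then gives a scale.

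**1. Classification under the rule**

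- Onset on or after first dose: TEAE.
- Condition present at Screening that worsens on drug: reportable as an AE under Protocol 8.1, and a TEAE if dated from the worsening. The dating convention is not stated.
- AE with known onset after consent and before first dose that worsens on drug: not a TEAE, unless re-recorded. No section requires re-recording.
- Onset date missing or partial: TEAE by default, unless the dates show that the event started or ended before study drug. SAP 7.1.2 asks whether "it can be conclusively established that the AE started prior to the start of study drug". Change in severity plays no part.

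The third case is the gap.

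**2. Outputs that lose the event, and outputs that keep it (SAP 7.5.1)**

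- Lost: TEAEs overall and by system organ class and preferred term; drug-related TEAEs; both worst-grade summaries; treatment-emergent SAE rows; the study-drug-discontinuation rows, table and listing; and the row for drug-related TEAEs leading to study discontinuation.
- Kept: the count of any AEs and the full AE listing. Where the event qualifies, also the any-SAE row, the all-SAE table and SAE listing, and the rows for AEs leading to study discontinuation or death.

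**3. Length of the window**

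Protocol 3.1 and Appendix A footnote a run the 96 hours from the standard-of-care blood draw. Protocol 6.2 places that draw before consent, and Protocol 3.1 allows consent only once yeast or a rapid test is positive. So

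consent-to-dose time ≤ 96 hours − (draw-to-consent time) < 96 hours.

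The documents do not give the draw-to-consent time, so the window cannot be stated more exactly.

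**4. Size per affected patient (n = 20)**

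Change in a preferred-term row = 1/20 = 5.0 percentage points, if the patient does not already have a TEAE under that term. With assumed counts and exact (Clopper-Pearson) 95% intervals:

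- 1/20 = 5% (0.1% to 24.9%)
- one patient added: 2/20 = 10% (1.2% to 31.7%)
- three patients added: 4/20 = 20% (5.7% to 43.7%)

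The overall TEAE count moves less readily. If 16 of 20 patients (assumed) already had some TEAE, only an affected patient among the other 4 would change it, from 16/20 = 80% to 17/20 = 85%.

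**5. Chance that anyone is affected**

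The per-patient probability q of such an event is an assumption; the documents give none. P(at least one in 20) = 1 − (1 − q)^20, and the expected number is 20q.

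- q = 1%: 18%, expected 0.2 patients
- q = 5%: 64%, expected 1 patient
- q = 10%: 88%, expected 2 patients

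**The case against.** The strongest reply is that the gap is narrow and mostly covered, and that several stronger readings fail. Much of this stands.

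- A reader might infer that serious events on drug go uncounted. They do not: all SAEs are tabulated by system organ class and preferred term whatever the onset, and AEs leading to death are also counted without the TEAE restriction. Among serious-event outputs, only the treatment-emergent SAE rows use the flag.
- A reader might take 96 hours as the consent-to-dose window. Step 3 of the working shows that it is shorter.
- A reader might see a contradiction between the protocol's worsening rule and the TEAE rule. Protocol 8.1 refers to signs or symptoms present at Baseline, which is Day 1 pre-dose, and could be read as reaching events that began after consent. An AE dated from its worsening is a TEAE under the present definition. What is shown is an unstated recording convention, not a direct contradiction. But the sentence opens with conditions present at Screening and sets no start date, so it does not settle TEAE status.
- A reader might say the SAP breaks its own worst-case principle. SAP 7.1.2 applies that principle only to missing or partial dates and makes no promise about events with a known pre-dose onset.
- Worsening in laboratory values, vital signs and ECG intervals is summarized against baseline in SAP 7.5.2 to 7.5.4, independently of the TEAE flag.

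What does not stand is that the listing and the any-AE count are enough. Neither gives an incidence of events worsening on drug by term, grade or relatedness, and with no control arm those tables carry the safety description.

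**Conclusion.** The concern holds in a limited form. Followed as written, the onset-only definition leaves out of the TEAE outputs any AE with a known onset between consent and first dose that worsens on APX001 and is not re-recorded. The error can only be downward. It is at most 5 points per affected patient in a preferred-term row at n of about 20, and zero in the overall TEAE count unless that patient has no other TEAE.

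It would be too strong to say that TEAE incidence is understated. That requires at least one such patient, and the documents give no basis for a rate; the 1% to 10% range is illustrative. The number affected is probably small, because onset must fall in a window shorter than 96 hours. The conclusion also assumes that sites keep a worsened event on its initial record. The documents neither require nor forbid this, and the eCRF completion instructions are not among them.

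This is a sound, low-cost correction to a safety definition. It does not affect the efficacy analysis.

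**What to change.** - **Definition.** In SAP 7.5.1 and Protocol 9.2.2, define a TEAE as an AE that starts on or after the first dose of study drug, or that starts before it and worsens in severity or seriousness on or after it.
- **Recording.** Instruct sites to open a new AE record, dated at the worsening, for any event that began before dosing and worsened afterwards. Apply the same convention to the worsened pre-existing conditions in Protocol 8.1, so that their start dates are consistent across sites. This step makes the definition programmable from dates.
- **Documentation.** If the protocol is not amended, record the change in SAP Section 9, which at present declares none.
- **Data already collected.** Review AEs with onset between consent and first dose by hand and query any that worsened. With about 20 patients and a short window this should be a brief list.

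The cost is one sentence in each document and an eCRF completion note, with no new patient assessments. TEAE counts may rise slightly. Patient counts are not inflated by the second record, because SAP 7.5.1 counts a patient once per preferred term. The overview's event counts would include both records, and a footnote should say so.
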